### **8.2. Risks to participation:**

- As a guard against *risk of breach of confidentiality*, all information will be stored in locked files in a locked research area that can only be accessed by research personnel. No names or identifying information will be used in publications that result from this research. Under no circumstances will identifying information be released to any outside party (beyond those immediately connected with the study) without written consent from the subject. In cases where data are stored on computers, no data containing identifiers or PHI will be stored on hard drives—only on removable media, which will be removed from the computer when not in use. All databases will be password protected.
- With regard to *risk of distress associated with interviews*, the participants will be told that they can stop the process at any point if they become overwhelmed or fatigued. Following their participation in the research, participants will be debriefed and have an opportunity to discuss their participation in the research and ask any questions they may have for the interviewer. If the patients are currently in psychiatric treatment, they will be encouraged to discuss any distress with their clinician (and with their permission we will provide feedback on the assessment to the treating clinician). If they are no longer in treatment, or if they request it, a list of resources (local mental health services) will be provided to them after participation. All subjects completing interviews and questionnaires will be provided with phone numbers so that they can have any questions answered that they feel have not been satisfactorily addressed. The investigative team has extensive experience, and they will determine if there is a need for clinical intervention; if necessary, arrangements for appropriate clinical services will be made.
- With regard to *risks associated with the acoustic startle response, electrodermal activity, and electrocardiogram recording*, if skin cleansing becomes uncomfortable for a given subject, the researcher will end the skin preparation at that point and apply the electrodes without further cleansing. The decibel levels and duration of the auditory stimuli are not sufficient to cause any damage to the ear. If a subject finds the noises too uncomfortable, the researcher will stop the experimental session immediately.
- With regard to *risk of dexamethasone administration*, no significant side effects have been observed in response to intermittent administration of dexamethasone (Decadron; Merck & Co., Inc., Whitehouse Station, NJ, <http://www.merck.com>). Decadron can cause anaphylactic shock in allergic patients and there are a wide range of side effects associated with prolonged administration. Participants will be carefully prescreened for allergies, pregnancy and other medical problems such as osteoporosis, diabetes, narrow-angle glaucoma, immunosuppressed state (e.g. HIV infection), and current infection that this medicine might affect before drug administration and a review of medical history and a physical exam will be performed by the study physician prior to study randomization

### **8.3 Benefits of Therapy:**

The benefit of this project to individual subjects is the potential for clinical improvement, which far outweighs the risks. This project's potential to contribute knowledge regarding this application and the ability of acute dosing with DEX to facilitate treatment of PTSD are considered significant benefits with no foreseen global risks. Participants have the opportunity to complete the entire, full package of PE, (12 sessions), thereby increasing the odds that each patient should benefit from participating in this study.

## 9.0 Data Collection:

The sources of research material collected from patients will include paper and pencil self-report questionnaires, information from structured interviews, psychophysiological measures (including heart rate, skin conductance, salivary cortisol, and startle), and clinician ratings of symptomatology. Assessment and treatment sessions will be videotaped to calculate inter-rater reliability of assessments and treatment compliance. All of the above will become part of each patient's research file. This data will be collected specifically for this research program. Data will be entered and stored electronically using REDCap, a secure, online database capture application (Harris et al., 2009). All information about individual participants, including the questionnaires, videotapes, assessment results, and therapy notes will be kept private, to the extent allowed by law. All information about participants (including videotapes) will be stored in locked file cabinets in locked offices. Videotapes will only be shared with other study staff to make sure treatment is being conducted correctly. Videotapes will contain initials rather than full names. Videotapes will be erased or destroyed 3 years after completion of the study.

## 10.0 Statistical Considerations

### 10.1 Preliminary Analyses

Premature Termination. Patients will be considered dropouts (a) if they miss two or more sessions or (b) if serious adverse reactions or clinical complications (e.g., suicidal intention) develop. Initial data analyses will be conducted on treatment completers. This will address relative efficacy among treatment completers. A second analysis will be conducted including all patients who initiate treatment using an intent-to-treat analysis. This will address relative efficacy in the population intended for treatment, thus incorporating issues related to potential differential dropouts in the treatment groups. Finally, analyses will be conducted to see if treatment completers differ from drop-outs on demographic variables and pre-treatment measures.

Group Equivalence. We will evaluate the effectiveness of random assignment to two treatment groups by comparing the groups on demographics, baseline measures of key outcome variables, and other important theoretical covariates. We will characterize differences between study dropouts and completers, and between dropouts from the VRE+DEX and VRE+placebo groups. We will compare dropouts to completers on the same set of baseline variables that will be used to examine initial group equivalence. Differences between conditions will be assessed using one way ANOVA for continuous variables and chi-square analyses for categorical variables (Fleiss et al., 2013). Any observed differences that approach statistical significance ( $P \leq 0.15$ ), and which are theoretically or empirically identified as potential confounders will be included as covariates in subsequent cross sectional and longitudinal analyses.

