## **2. Objectives**

### **Specific Aims and Research Hypotheses**

The proposed study is designed to achieve the following specific aims:

**Aim 1.** To explore whether dexamethasone (DEX), a cortisol analogue, administered 10+ hours prior to the virtual reality exposure (VRE) therapy session, enhances exposure therapy in humans with PTSD as compared to pill placebo;

**Aim 2.** To explore whether any enhancement in exposure therapy produced by DEX in VRE evidenced within session and immediately post-treatment results in long-term gains in treatment response as compared to pill placebo.

*The following hypotheses will be tested:*

- 1) DEX will facilitate fear extinction in humans. It is predicted that the patients who receive VRE combined with 0.5 mg DEX + 10hr will evidence more improvement on symptom measures, and on reduced psychophysiological arousal measured via startle, skin conductance, and heart-rate responses during exposure to Iraq or Afghanistan military scenes, than the placebo group. Furthermore, DEX + VRE will result in faster improvement in symptoms (fewer sessions to reach 70% reduction in symptoms), and fewer drop-outs (i.e., better tolerance of exposure therapy).
- 2) Facilitation of therapeutic response aided by DEX will result in long-term gains. It is predicted that the group of patients who receive VRE combined with 0.5 mg of DEX will evidence more improvement on a follow-up assessment gathered 3, 6, and 12 months post-treatment as compared to baseline on symptom measures and reduced startle, skin conductance, and heart-rate responses during exposure to Iraq or Afghanistan military scenes than the group who receives placebo.

Exploratory analyses of genetic markers will examine predictors of treatment response. The long-term goals include furthering translational research and directly applying paradigms shown successful in animals to humans. For this specific paradigm, we plan to establish whether DEX can facilitate exposure therapy and apply this knowledge to other disorders. Random assignment of participants to placebo or active conditions, standardized treatment delivery, homogeneous DSM inclusion criteria, and blind independent assessment will assure a methodologically rigorous study.

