#### **6.0 Therapy**

Treatment will commence following the pre-treatment assessment and all participants will be then randomized and seen for an introductory session and then treated once or twice per week for 6-11 therapy sessions, including one information gathering and preparation for VRE sessions. Patients will be randomized to receive dexamethasone or pill placebo before the VRE sessions. VRE will be limited to a minimum of 6 sessions and a maximum of 11 sessions, based upon reaching criterion of 70 % symptom improvement as indicated on the PTSD Symptom Scale or an agreement between clinician and participant that maximum treatment response has been achieved. All sessions will be individual and weekly or twice weekly. The first session will last approximately 90 minutes and will be spent in information gathering, treatment planning, and explaining the treatment rationale to the patient. Information gathering will review the history of PTSD and their military service and will include a brief psychosocial history, including review of prior treatment. The VRE sessions will last 90-minutes each. During VRE sessions patients will wear a head-mounted display with stereo earphones that will provide visual and audio cues consistent with Iraqi or Afghan military scenarios. The therapist will make appropriate comments and encourage continued exposure until anxiety has habituated. During exposure, information will be gathered on the participant's anxiety level through the use of a 0-100 SUDs scale. All therapists will have been trained in Prolonged Imaginal Exposure therapy (PE) followed by training in VRE by Drs. [name] and [name]. Drs. [name] and [name] will supervise all therapy.

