Continuous variables will be analyzed using multivariate repeated measures ANCOVA with treatment condition being the between subjects factor, the pre-treatment vs. post-treatment condition being the within subjects factor, and the scale scores as the multiple measures accounting for appropriate covariates as determined through preliminary analyses discussed above. Adjusted means and mean differences as well as interaction terms will be obtained and evaluated. Categorical variables will be analyzed using logistic regression and controlling for appropriate covariates resulting in adjusted odd ratios.

An additional approach to testing this hypothesis will involve using two categorical measures of clinically significant improvement: 1) a 30% decrease in the CAPs, and 2) a rating of “much improved” or “very much improved” by the therapist and participant on the CGI inventory at the end of active treatment. These data will be analyzed using logistic regression with the inclusion of appropriate terms for the covariates and treatment-by-covariate interactions.

Furthermore, we will look at the number of sessions required to reach 70% improvement or maximum treatment response and the number of dropouts, predicting fewer sessions to reach 70% improvement or maximum treatment response and fewer dropouts in the VRE + DEX group.

Within-subject measures will also be obtained to assess improvement within sessions. SUDS and psychophysiological measures (heart rate and skin conductance) will be used to measure within session anxiety levels. Average and peak values of these continuous variables will also be analyzed using a repeated measures ANCOVA.

Hypothesis 2: Patients who receive VRE+DEX will evidence more improvement on follow-up assessments (symptom measures and psychophysiological responses) gathered 3, 6 and 12 months post-treatment compared to the patients who receive the placebo.

*Interval specific analyses:* First, the effectiveness of the VRE+DEX treatment will be analyzed for the two interval periods separately: from immediately post-treatment to the 3, 6 and 12 -month assessment. To test these time interval specific treatment effects, logistic regression will be used to compute adjusted odd ratios for dichotomous outcomes and multivariate

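### The two-missed-sessions dropout rule ignores course length, so a faster-responding DEX arm would show fewer dropouts with no difference in tolerance

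*Combined protocol and SAP*

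**What the plan says.** Section 10.1 (Premature Termination) gives two grounds for the dropout label. The first reads: "Patients will be considered dropouts (a) if they miss two or more sessions". Ground (a) is thus a fixed count. It is not tied to the number of sessions due, and nothing is said about visits that are rescheduled and then attended. The second, ground (b), applies "if serious adverse reactions or clinical complications (e.g., suicidal intention) develop".

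Section 6.0 makes the length of treatment variable: "VRE will be limited to a minimum of 6 sessions and a maximum of 11 sessions". Within that range, response decides when treatment ends. One route is stated as "based upon reaching criterion of 70 % symptom improvement as indicated on the PTSD Symptom Scale". The other is a joint judgement by clinician and participant that the maximum response has been reached. The first session is preparatory, which leaves 5 to 10 exposure sessions.

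Hypothesis 1 (section 2) predicts faster improvement under DEX and also "fewer drop-outs (i.e., better tolerance of exposure therapy". The Hypothesis 1 analyses in section 10.2 repeat the pair, "predicting fewer sessions to reach 70% improvement or maximum treatment response and fewer dropouts in the VRE + DEX group".

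On populations, section 10.1 says "Initial data analyses will be conducted on treatment completers", followed by "A second analysis will be conducted including all patients who initiate treatment using an intent-to-treat analysis". Completer has no definition of its own. Section 10.1 also compares dropouts with completers, and dropouts between the arms.

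**The concern.** The number of opportunities to miss a session is itself an outcome. A patient who responds quickly can leave after 6 sessions, while a slow responder may be scheduled for 11. With the same chance of missing any one session, the slow responder is more likely to accumulate two misses.

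The plan predicts that DEX shortens the course. If it does, the rule produces fewer dropouts on DEX through shorter exposure alone. The second prediction then partly restates the first, and the plan's reading of it as tolerance does not follow.

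The same label appears to determine who is a completer. A patient who misses two visits out of a long course and still reaches an end-of-treatment condition could therefore be left out of the efficacy analysis that is done first.

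**Working it through.** **The plan's own figures.** No figure is stated for this rule. The one computed figure, 85% power for d = .65 with 100 participants, reproduces once the stated 10% loss is taken off: with 45 per arm, 0.65 × √(45/2) − 1.96 = 1.12, giving about 87% (86% with the t distribution). Nothing below depends on it. The relevant benchmark in section 10.2 is the assumed 15% who drop out of treatment. The 25% total also includes 10% lost to measurement, which is a different event.

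**Inputs.** Sessions k = 6 to 11 (section 6.0); label at two or more misses (section 10.1); 50 per arm and two-sided 0.05 (section 10.2). The per-session miss probability p is not in the documents. I assume that it is equal in both arms, constant, and independent across sessions, and I show a range.

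**Chance of the label over k scheduled sessions:** P = 1 − (1 − p)^k − k·p·(1 − p)^(k−1).

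For p = 0.10 and k = 6: 1 − 0.5314 − 0.3543 = 0.114.

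| p | 6 sessions | 11 sessions | ratio |
|---|---|---|---|
| 0.05 | 3.3% | 10.2% | 3.1 |
| 0.10 | 11.4% | 30.3% | 2.6 |
| 0.15 | 22.4% | 50.8% | 2.3 |

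If only the 5 to 10 exposure sessions can be missed, the corresponding pairs are 2.3% v 8.6%, 8.1% v 26.4% and 16.5% v 45.6%. The pattern is the same.

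**A less extreme case, anchored to the plan.** Solving P = 0.15 at k = 8 gives p ≈ 0.087. At that p:

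| sessions | 6 | 7 | 8 | 9 | 10 | 11 |
|---|---|---|---|---|---|---|
| labelled dropout | 9.0% | 11.9% | 15.0% | 18.2% | 21.5% | 24.9% |

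Each extra session adds about 3 percentage points. Because the rise is almost linear, using one course length per arm is a fair stand-in for a spread around that mean.

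For 8 v 10 sessions the expected counts are 7.5 v 10.7 of 50. Under the normal approximation, the pooled standard error is √(2 × 0.1825 × 0.8175/50) = 0.0773 and the unpooled is 0.0770. So (0.065 − 1.96 × 0.0773)/0.0770 = −1.12, and the comparison is significant about 13% of the time in the direction favouring DEX. For 7 v 9 sessions the figure is about 14%. Only the extreme, 6 v 11, reaches about 56%.

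**If missed visits are made up** until k have been attended, the chance of the label is 1 − (1 − p)^k − k·p·(1 − p)^k. This gives 4.4% v 11.8% at p = 0.05 and 15.0% v 34.1% at p = 0.10 (6 v 11). On this reading every patient labelled under ground (a) has attended the full course.

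**With a common window** of the first six scheduled sessions, the chance at equal p is the same in both arms whatever the speed of response (3.3%, 11.4% and 22.4% at the three rates above), so the exposure effect is zero.

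**The case against.** - **The effect is conditional.** It needs DEX to shorten treatment. A reader might infer that the rule inflates the false-positive rate generally. It does not: with equal speed in the two arms the expected dropout shares are equal. This stands.
- **The size is modest in realistic cases.** Comparing 6 with 11 sessions puts every patient in one arm at the minimum and every patient in the other at the maximum, which the plan nowhere predicts. A two-session difference moves about three patients in 50. This stands. Misses may also cluster in patients who are disengaging, so independence is only a working assumption.
- **A reader might infer that the rule alone explains the plan's 25% non-completion.** The comparable quantity is the 15% treatment dropout, as shown above.
- **Removal of finishers is not established.** The rule sits under a heading about premature termination. If it is an operational stop at the second miss, nobody so labelled finishes. A rescheduled visit may also not count as missed. The text settles neither point. The exposure effect remains under the operational reading.
- **Safeguards exist.** There is a second analysis of all who start treatment, and section 10.2 continues measurement after dropout. These protect the intent-to-treat efficacy result. They do not repair the dropout count, the completer set or the dropout comparisons in section 10.1, all of which use the label.
- **The study is a pilot with exploratory aims**, and no formal test is named for the dropout count. This lowers the stakes, but the prediction and its reading as tolerance are written into Hypothesis 1.

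**Conclusion.** The point holds as one of interpretation. If DEX speeds response, the planned dropout comparison mixes tolerance with course length, in exactly the scenario that the plan predicts. A lower count on DEX could not be read as better tolerance. If DEX does not change speed, the comparison is unbiased.

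At a miss rate consistent with the plan's own 15%, a two-session difference produces a gap of about 6.5 percentage points with no difference in tolerance. Larger gaps need higher miss rates or larger differences in course length. All sizes rest on an assumed miss rate that is equal between arms and independent across sessions.

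Exclusion of patients who finish from the completer analysis is possible if the rule is an analysis label, but section 10.1 does not say that it is. A reader might go further and infer that the completer efficacy estimate is materially biased. The documents do not support that: slow responders would be removed from both arms, and no size for such a bias has been shown.

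**What to change.** Change the analysis text only. Any clinical rule for stopping treatment stays as it is.

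1. Compare dropout between arms over the first six scheduled sessions, which are due for every patient under the section 6.0 minimum.
2. As support, report the per-session discontinuation rate by arm over the full course, for example from a discrete-time logistic model with session number, alongside the number of sessions due.
3. Define a completer as a patient who reaches one of the end-of-treatment conditions in section 6.0, and record which one. Keep ground (b) of section 10.1 in the dropout definition.
4. State whether a rescheduled visit counts as missed, and whether ground (a) is an analysis label or an operational stop. Sections 6.0, 10.1 and 10.2 should agree on this.

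The cost is wording, settled before unblinding; section 6.0 (Patient Compliance) already tracks attendance. There are three limits. The six-session window ignores later dropout. The per-session rate conditions on response after randomisation, which is why both should be reported. And one end condition is a joint judgement of clinician and participant, so an early stop could be recorded as completion; recording the condition met makes this visible.

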### 10.2 Statistical Analyses

#### Power and Sample Size

Power calculations are based on Cohen (1992). We set the Type I Error rate at 0.05 (two-tailed) for all computations. We first calculated the number of participants needed to test the effect of VRE augmentation with DEX at immediate post-treatment assessment (Hypothesis 1 above). Then, knowing how many participants would be needed at the end of this phase, we worked backward to calculate how many participants would need to be enrolled initially. We will continue to collect data from all participants, including those who drop out of treatment or are discontinued. Thus, loss to the study represents a failure to participate in measurement, and not merely dropout from treatment. We assumed that: (1) 10% of participants will be lost to the

study by the end of treatment; an additional 15% of participants will drop out of treatment, resulting in 25% of participants randomized to placebo or 0.5mg DEX groups that would not complete treatment. We anticipate that 10% of completers will be lost to the study prior to the 3 month follow-up visits.

The effect size measure used,  $d$ , represents the standardized difference between sample means. Cohen (1988) has proposed that  $d = .30$ ,  $.50$ , and  $.80$  be categorized as “small,” “medium,” and “large,” respectively. We assume that a medium effect size—half a standard deviation—is the smallest clinically meaningful difference between DEX-augmented VRE vs. placebo-augmented VRE at the end of treatment.

For a two-group study design, 100 participants ( $n=50$  in each group) would be needed to achieve a minimum desired power of 85% to detect an effect size of  $.65$  with a 2-sided test at a significance level of 0.05.

Hypothesis 1: Patients who receive VRE+DEX will evidence more improvement on within-session measures (SUDs), on immediate post-treatment symptoms measures and on startle, SCR and HR, than the group who receives placebo.

To analyze pre-treatment and immediate post-treatment differences, the first analysis will compare the VRE+DEX condition to the VRE+placebo condition on the following outcome measures: 1) symptom measures (continuous variables); 2) psychophysiological measures (startle responses, cortisol levels, heart-rate, skin conductance) (continuous variables). It is expected that VRE+DEX participants will show significant improvement on all outcome measures immediately post-treatment compared to VRE+ placebo participants.

Continuous variables will be analyzed using multivariate repeated measures ANCOVA with treatment condition being the between subjects factor, the pre-treatment vs. post-treatment condition being the within subjects factor, and the scale scores as the multiple measures accounting for appropriate covariates as determined through preliminary analyses discussed above. Adjusted means and mean differences as well as interaction terms will be obtained and evaluated. Categorical variables will be analyzed using logistic regression and controlling for appropriate covariates resulting in adjusted odd ratios.

An additional approach to testing this hypothesis will involve using two categorical measures of clinically significant improvement: 1) a 30% decrease in the CAPs, and 2) a rating of “much improved” or “very much improved” by the therapist and participant on the CGI inventory at the end of active treatment. These data will be analyzed using logistic regression with the inclusion of appropriate terms for the covariates and treatment-by-covariate interactions.

Furthermore, we will look at the number of sessions required to reach 70% improvement or maximum treatment response and the number of dropouts, predicting fewer sessions to reach 70% improvement or maximum treatment response and fewer dropouts in the VRE + DEX group.

Within-subject measures will also be obtained to assess improvement within sessions. SUDS and psychophysiological measures (heart rate and skin conductance) will be used to measure within session anxiety levels. Average and peak values of these continuous variables will also be analyzed using a repeated measures ANCOVA.

Hypothesis 2: Patients who receive VRE+DEX will evidence more improvement on follow-up assessments (symptom measures and psychophysiological responses) gathered 3, 6 and 12 months post-treatment compared to the patients who receive the placebo.

*Interval specific analyses:* First, the effectiveness of the VRE+DEX treatment will be analyzed for the two interval periods separately: from immediately post-treatment to the 3, 6 and 12 -month assessment. To test these time interval specific treatment effects, logistic regression will be used to compute adjusted odd ratios for dichotomous outcomes and multivariate

repeated measures ANCOVA will be used to obtain adjusted means, mean differences and interaction terms for continuous outcomes. For each of these analyses, the baseline measure for each specific outcome will be included as a covariate in the analysis.

*GEE Modeling for analysis of entire 12-month assessment period:* Additionally, to evaluate treatment effects for the entire 12-month follow up period, logistic and linear generalized estimating equation (GEE) regression models will be used for dichotomous and continuous variables respectively. GEE modeling is an appropriate analytic tool for longitudinal, repeated measures data as it is designed to adjust for within-subject correlations over time (Liang & Zeger, 1986; Kleinbaum et al., 1998; Hardin & Hilbe, 2003). By using the GEE method, the relationship between outcome variables obtained at different assessment time points and predictor variables are analyzed simultaneously. GEE models are comprised of a time independent variable (i.e. treatment condition) and a time-dependent variable (i.e. key outcomes variables and covariates). The estimated coefficients reflect the relationship between the time-independent and time-dependent using all available longitudinal data. Since repeated observations within one subject are not independent of each other, a correction must be implemented to account for within-subject correlations. This correction is achieved by assuming an a priori correlation structure for the repeated measurements of the outcome variables. It is proposed that the autoregressive correlation structure will be utilized. The assumption behind the autoregressive correlation structure is that the correlation between responses is dependent on the interval of time between responses. The resulting GEE parameters can be interpreted as the odds or the mean difference for logistic and linear regression models respectively, over the entire 12-month period for an average participant. GEE analyses will be performed using STATA, version 8.0 (Stata Press, College Station, Texas) using the xtgee command with corr(ar1).

*Security.* A participant will be identified throughout the central database by his or her unique subject identification number (SID). Information which could identify a subject, such as name, address or social security number, will either not be stored electronically or will be kept in files on a separate machine and network from the database files containing study data. All subject paper files will be stored in locked cabinets at all times. All computer systems and programs will be password protected. All network-based communications of study and other confidential information will be encrypted. Good computer security practice (shutting down of computer after work hours, restricting physical access to machines, prohibition of password sharing) will be required of all study personnel. Virus protection software will be installed on each study machine. The virus detection tools will be used, maintained, audited and, if necessary, updated on all computers and pathways into the system. Redundant backups will allow for quick restoration of data in the unlikely event that a hardware failure or security breach should occur. Periodically, database files will be archived onto compact discs and stored offsite.

*Archiving.* All study raw data, forms, documents, software programs, software applications and computer data files will be indexed and archived routinely. Strict version control of documents and software applications will be instituted. At the completion of the study, primary study documentation will be consolidated and retained in filing cabinets in an organized fashion, with a clear index to organization.

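### Should the power paragraph be changed because it sizes the trial for d = 0.65 after calling d = 0.50 the smallest meaningful difference?

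*Combined protocol and SAP*

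**What the plan says.** Section 10.2 (Power and Sample Size) sets a two-sided type I error of 0.05 and describes the order of the calculation: "We first calculated the number of participants needed to test the effect of VRE augmentation with DEX at immediate post-treatment assessment", then back from that number to the number enrolled. It assumes that 10% are lost to the study by the end of treatment and that a further 15% drop out of treatment, "resulting in 25% of participants randomized to placebo or 0.5mg DEX groups that would not complete treatment". It separates the two kinds of loss: "We will continue to collect data from all participants, including those who drop out of treatment or are discontinued", and "loss to the study represents a failure to participate in measurement, and not merely dropout from treatment".

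On effect size, it states that half a standard deviation "is the smallest clinically meaningful difference between DEX-augmented VRE vs. placebo-augmented VRE at the end of treatment". The next paragraph says that 100 participants (50 per group) "would be needed to achieve a minimum desired power of 85% to detect an effect size of" 0.65. No sentence connects 0.50 with 0.65.

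Section 10.1 (Preliminary Analyses) gives the order of the analysis sets. "Initial data analyses will be conducted on treatment completers" comes first, followed by "A second analysis will be conducted including all patients who initiate treatment using an intent-to-treat analysis".

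**The concern.** A stated smallest meaningful difference in a power section is normally the value the trial is sized to detect. Here it appears and is then passed over for a value 0.15 SD larger, with no pilot estimate or other argument. A reader could take the 85% to cover d = 0.50, which it does not.

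The order of the analysis sets adds to the doubt. The completer analysis is run first, yet the plan's own 25% non-completion leaves it smaller than the set for which 85% holds. If the true effect is d = 0.50, an unadjusted comparison would miss it about 35% of the time with 90 measured, and about 43% of the time with 75 completers. What is at stake is how a non-significant result is read: it could be given more weight against d = 0.50 than the trial can support.

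**Working it through.** **Inputs** (Section 10.2, Power and Sample Size): two-sided alpha 0.05; target power 85%; d = 0.65 for sizing; d = 0.50 as the minimum meaningful difference; 100 enrolled, 50 per group; 10% lost to measurement; 25% not completing treatment.

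**The plan's own figure.** For two means with SD 1, the normal approximation is n per group = 2(z₀.₉₇₅ + z₀.₈₅)²/d² = 2(1.960 + 1.036)²/0.65² = 42.5, so 43; the exact t calculation gives 44. Allowing for 10% loss, 44/0.90 = 48.9, so 49 per group and 98 in total, close to the stated 100. Other readings fit less well: with no loss the total is 86 to 88, and with 25% inflation it is 115 to 118. The figure therefore corresponds to participants measured post-treatment, which is also what the section's definition of loss implies. The section does not name the set, so this is an inference.

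**Power by set.** Noncentral t with noncentrality d√(n/2) and 2n − 2 degrees of freedom, unadjusted:

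| Set | n per group | d = 0.65 | d = 0.50 |
|---|---|---|---|
| All enrolled, no loss | 50 | 89.6% | 69.7% |
| Measured: 100 × 0.90 = 90 | 45 | 86.2% | 65.0% |
| Completers: 100 × 0.75 = 75 | 37.5 | 79.3% | 57.0% |

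For the measured set the noncentralities are 0.65 × √22.5 = 3.08 and 0.50 × √22.5 = 2.37. The completer row assumes the same d in completers as in everyone measured. An unequal 40/35 split of completers gives 79% and 57%, so imbalance hardly matters. The effect detectable with 85% power is 0.64 in the measured set and 0.70 in completers.

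**What an estimate would show.** The 95% confidence interval half-width is t₀.₉₇₅ × √(2/n): 0.42 SD with 45 per group and 0.46 SD with 37.5. An observed difference of 0.50 SD would therefore be significant in either set.

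**What sizing for 0.50 would take.** 85% power needs 73 per group; 73/0.90 = 81.1, so 82 per group and 164 enrolled, against 100 planned.

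**Effect of the planned model.** The documents give no pre-post correlation r, so r is assumed at 0.3 / 0.5 / 0.7. For d = 0.50 in the measured set, a baseline-adjusted univariate test (effect d/√(1 − r²)) has power 69 / 77 / 91%. A univariate change-score test (effect d/√(2(1 − r))) has 51 / 65 / 86%. Section 10.2 plans a multivariate repeated measures ANCOVA with several scales as the measures, and it gives no correlations between scales. Neither row is therefore the power of the planned test. They show only that adjusted power cannot be fixed from the documents.

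**The case for a change.** The strongest case for a change is that it would cost almost nothing. The sample size would stay at 100, one sentence would justify 0.65, and a second would give the power at 0.50 and say that a null result does not rule it out. The pilot title and the exploratory wording of the aims do not fully answer this, because the Summary also calls the trial an efficacy study and Section 10.2 makes a formal power claim.

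Much of this stands. The step from 0.50 to 0.65 is unexplained, the power at 0.50 is modest, and the completer set falls short of 85% even at 0.65. The argument does not show that anything stated is wrong or that any result would differ. A design alternative may exceed the smallest difference of interest. The completer analysis comes first in order, but no set is called primary, and the sizing was for measured participants. The documents nowhere say that a non-significant result will be taken to exclude d = 0.50, so the feared misreading is a possibility and not something the plan commits to.

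Writing more figures in also carries risk. Calling the 90 measured participants the intent-to-treat set would conflict with Section 10.1, which includes everyone who starts treatment. Adjusted power at assumed correlations would suggest a precision that the documents cannot support.

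**Conclusion.** No change is needed. The stated 85% holds for d = 0.65 (86% with 45 per group, unadjusted) in the set that the plan's definition of loss implies. What is missing is a rationale for 0.65 and a power figure for d = 0.50, which is about 65% with 90 measured and 57% with 75 completers. Both can be worked out from the plan's own inputs, and neither alters the sample size, the test, the analysis sets or the results. Whoever reports the trial can read a non-significant result from its confidence interval, with an expected unadjusted half-width of 0.42 to 0.46 SD.

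This conclusion rests on three assumptions: the 85% refers to participants with a post-treatment measurement, the comparison is an unadjusted two-group t-test, and d is the same in completers as in all those measured. It would be different if the plan claimed 85% for d = 0.50, or if it said that a null result would rule that difference out. It does neither.
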